clinical course endpoints. Based on all clinical course data from Cohort 2 available at the time of the cut-off for the third IA, one or more clinically relevant endpoint(s) will be selected for confirmation in the final analysis. Time to resolution (i.e. to none or mild symptoms) and reduction in severity of selected clinical signs/symptoms of RSV-related illness are currently expected to be the most relevant clinical endpoints for Phase 3 planning. However, data from this study, in combination with data from other RSV studies within and outside the company, and knowledge obtained through health authority interaction(s) will be considered in IA#3 for the endpoint selection and sample size recalculation for Cohort 2. After selection of (a) clinical endpoint(s), the number of subjects in Cohort 2 will be calculated that is required to minimize the conditional probability of inconclusive results (within the Go-NoGo approach) at the end of the study, assuming a required confidence of 80% (2-sided) to exclude the target value and/or the minimum acceptable value.

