The difference between each active treatment group versus placebo will be derived using appropriate contrasts for Day X, Day 8 and Day 10 (PRESORS ObsRO only) from the same model containing all PRESORS ObsRO/ClinRO assessments from baseline through assessment day of interest (ObsRO: Day 10, ClinRO: Day 8).

The aforementioned will be presented for the subgroups as defined in Section 2.4.

RSV-related Complications

RSV-related complications will be provided based on the original (investigator assessment) and modified (study physician-identified complications) definitions.

Original Definition (Investigator Assessment):

The proportion of subjects with a complication (Yes and No) will be shown in a frequency tabulation including corresponding 95% CI by treatment as based on the Wilson score test.

Based on the binary categorization (Yes vs No), the difference in proportion of subjects with RSV-related complications, as assessed by the investigator, between each active treatment group as compared to placebo will be investigated. Frequency procedure in SAS® provides Newcombe confidence limits with Mantel-Haenszel weights for the common risk difference (difference in proportion of subjects with RSV-related complications), controlling for the two randomization stratification factors (separately). The difference in proportion of subjects with RSV-related complications and 80% and 95% 2-sided confidence intervals for this point estimate, controlling for randomization stratification factors, will be presented.

Similar frequency tables will be provided for the subcategories.

The aforementioned summary will be presented overall by treatment group and by the subgroups as defined in Section 2.4.

Modified Definition (Study Physician-identified Complications):

The number (n) and percentage (%) of subjects in the ITT-i analysis set with RSV-related complications (Yes vs No) will be presented, as frequency tabulation. The incidence will

be presented for emergent adverse events (treatment phase and follow-up phase), as assessed by the study physician (modified definition), occurring during the study and treatment phase only.

The number (n) and percentage (%) of subjects, by MedDRA preferred term, in each of the subcategories will also be presented.

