5.6. Decision Rules at Interim Analyses

During IAs, the primary viral load endpoint and 3 below-mentioned key clinical course endpoints are considered. Minimum acceptable value and target value for these key clinical course endpoints are defined in [Table 23](#):

Table 23: MAV and TV

Endpoint	Minimum Acceptable Value (MAV)	Target Value (TV)
Time to resolution of key RSV symptoms (ObsRO)	No difference (MAV = 0)	1 day (24 hours) reduction (TV = -1)
Change from baseline (CFB) in summary parameter: key RSV symptoms (ObsRO) at Day 8	No difference (MAV = 1)	20% larger change from baseline, where the change from baseline represents a reduction in score (TV = 1.2*)
Incidence of RSV-related Complication	No difference (MAV = 0)	10% absolute reduction in rate (TV = -0.1)

* This represents a 20% increase in the magnitude of the CFB and not in the summary parameter score itself (i.e. if the CFB in the Placebo treatment group is -1.0, then the target CFB for the active treatment group would be -1.2)

Note that the viral load endpoint will be evaluated on a combined dataset of both cohorts for each interim analysis, except for IA#1 where only Cohort 1 data are available. Clinical course endpoints will be evaluated in the community cohort only for IA#3 and IA#4.

For IA#3 and IA#4 analyses, in case of severe imbalance between ≤ 3 days and > 3 days since symptom onset and where there are more subjects in the > 3 to ≤ 5 days stratum than in the ≤ 3 days stratum (i.e. $> 55\%$ of subjects in the > 3 to ≤ 5 days stratum), a second analysis will be conducted considering 50% of subjects randomized in each stratum (symptom onset ≤ 3 days and symptom onset vs > 3 to ≤ 5 days) in each cohort separately. Chronological order of randomization (date and time) per stratum will be followed when defining the balanced dataset. In case there are inconsistencies in the results between the complete and the balanced analysis, no decision on altering the study (i.e. stopping for futility or enriching) will be taken and the study will proceed as planned and collect more data. In the case that a balanced analysis has been carried out (as described above), the sample size re-estimation at IA#3 will be performed on the balanced dataset only.

The IDMC will provide recommendations to the SC according to the below guidance:

Interim Analysis 1

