- The time to resolution of key RSV symptoms will be analyzed using an accelerated failure time (AFT) model, using the log-logistic distribution as described in Section 5.3.2.2. However, the term for baseline \log_{10} viral load will be retained whether or not it is significant at the 10% significance level. The median time to resolution for the placebo group (T_p) in days will be estimated based upon this model and the TV that corresponds to a 1-day reduction for the high dose group will be calculated as a log relative reduction (i.e. as $\log[(T_p-1)/T_p]$). The MAV of no difference corresponds to a log relative reduction of $\log(T_p/T_p) = 0$. The 1-sided p-values for the tests to compare the difference between the high dose and placebo groups versus the TV and MAV will be derived using normal approximations for appropriate contrasts, Z_{TV} and Z_{MAV} .

Change from baseline in key RSV symptoms at Day 8

- The change from baseline in key RSV symptoms at Day 8 will be analyzed using a restricted maximum likelihood repeated measures approach as described in Section

5.3.2.2. The adjusted mean reduction from baseline for the placebo group will be estimated based upon this model (\bar{x}_P) and the TV that corresponds to a 20% larger change from baseline for the high dose group (i.e. $1.2\bar{x}_P$) will be calculated. The MAV corresponds to a difference in the change from baseline of 0 (i.e. $1.0\bar{x}_P$). The 1-sided p-values for the tests to compare the difference between the high dose and placebo groups versus the TV and MAV will be derived using normal approximations for appropriate contrasts, Z_{TV} and Z_{MAV} .

Incidence of RSV-related complications

- The 1-sided p-values to compare the proportion of subjects with at least one RSV-related complication between the high dose and placebo groups versus the MAV and TV will be derived using a normal approximation to the binomial distribution; where:

$$\hat{p}_1 - \hat{p}_2 \sim N \left(p_1 - p_2, \frac{p_1(1-p_1)}{n_1} + \frac{p_2(1-p_2)}{n_2} \right)$$

The TV of an absolute reduction in rate of 10% corresponds to a difference in the proportion of subjects with at least one RSV-related complication in high dose versus placebo of -0.1. The MAV corresponds to a difference in the proportions of 0.

For each of the three clinical course endpoints, the conditional probability for the Stop decision for the situation without/with enrichment and for each assumed total sample size will be calculated as:

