
- $CP_{x;Stop} = 1 - \Phi \left(\frac{\Phi^{-1}(0.9) - \sqrt{w_1} \Phi^{-1}(1-p_{Full;TV})}{\sqrt{1-w_1}} - \sqrt{\frac{n_2}{n_{1,x}}} \Phi^{-1}(1-p_{x;TV}) \right)$

The conditional probability for the Go decision for the time to resolution of key RSV symptoms and the incidence of RSV-related complications will be calculated as:

- $CP_{x;Go} = \Phi \left(\min \{ CRV_{TV} - \mu_{x;TV}, \mu_{x;MAV} - CRV_{MAV} \} \right)$

where:

- $CRV_{TV} = \frac{\Phi^{-1}(0.9) - \sqrt{w_1} \Phi^{-1}(1-p_{Full;TV})}{\sqrt{1-w_1}}$ and $CRV_{MAV} = \frac{\Phi^{-1}(0.9) - \sqrt{w_1} \Phi^{-1}(1-p_{Full;MAV})}{\sqrt{1-w_1}}$
- $\mu_{x;TV} = \sqrt{\frac{n_2}{n_{1,x}}} \Phi^{-1}(1-p_{x;TV})$ and $\mu_{x;MAV} = \sqrt{\frac{n_2}{n_{1,x}}} \Phi^{-1}(1-p_{x;MAV})$
- x corresponds to the decision not to enrich / to enrich at #IA3
- $p_{x;TV}$ and $p_{x;MAV}$ represents p-values for the population of interest (full population for no enrichment and sub population for enrichment).
- $n_{1,x}$ represents the number of randomized patients in Cohort 2 at the time of IA#3 for the population of interest.

- n_2 represents the number of additional patients to be included in Cohort 2 up until the end of the study (i.e. $N - n_{1,Full}$, where N represents the total number of randomized subjects in Cohort 2 at the end of the study).
- $w_1 = n_1 / n_{Primary}$ where $n_{Primary} = 225$ is defined as midway between the planned sample size ($N=150$) and the maximum sample size ($N=300$) for Cohort 2.

The conditional probability of the Go decision for the change from baseline in key RSV symptoms at Day 8 needs to take the correlation, ρ , of Z_{TV} and Z_{MAV} into account.

$$\rho = -\frac{\left(\frac{1}{n_{H1,x}} + TV * MAV \frac{1}{n_{P1,x}}\right)}{\left(\sqrt{\frac{1}{n_{H1,x}} + TV^2/n_{P1,x}}\right)\left(\sqrt{\frac{1}{n_{H1,x}} + MAV^2/n_{P1,x}}\right)}$$

The conditional probability of the Go decision is calculated using a bivariate normal distribution where:

- $CP_{x;Go} = P(Z_{x2;TV} < CRV_{TV} \cap Z_{x2;MAV} > CRV_{MAV}; \mu = (\mu_{x;TV}, \mu_{x;MAV}), \rho)$

Where:

- $n_{H1,x}$ represents the number of Cohort 2 subjects in the high dose group that were included in the analysis at IA#3 for the population of interest.
- $n_{P1,x}$ represents the number of Cohort 2 subjects in the placebo treatment group that were included in the analysis at IA#3 for the population of interest.

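### The target value for time to resolution is built from the estimated placebo median, but the Interim Analysis 3 Go formula treats it as known

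*SAP*

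**What the plan says.** SAP Section 5.6 (Table 23) gives the TV for time to resolution of key RSV symptoms as "1 day (24 hours) reduction (TV = -1" day). For Interim Analysis 3 (IA#3) this absolute target is moved to the log scale. "The median time to resolution for the placebo group", Tp, is estimated from the accelerated failure time (AFT) model, and the TV "will be calculated as a log relative reduction", that is log[(Tp−1)/Tp]. One-sided p-values against the TV and the minimum acceptable value (MAV) come from normal approximations for contrasts Z_TV and Z_MAV. No variance is written out for Z_TV.

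The nominal level follows from Section 1.4, "assuming a required confidence of 80% (2-sided) to exclude the target value and/or the minimum acceptable value", and from Φ⁻¹(0.9) in the Section 5.6 formulas: 10% one-sided.

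Two Go formulas are given. "The conditional probability for the Go decision for the time to resolution of key RSV symptoms and the incidence of RSV-related complications" is Φ(min{CRV_TV − μ_TV, μ_MAV − CRV_MAV}). By contrast, "The conditional probability of the Go decision for the change from baseline in key RSV symptoms at Day 8 needs to take the correlation" of Z_TV and Z_MAV into account, through a bivariate normal whose Z_TV variance term is 1/n_H + TV²/n_P.

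For complications the TV is a fixed −0.1, and the p-values "will be derived using a normal approximation to the binomial distribution" with plug-in variances. Section 5.4.2 plans the 80% interval for the same endpoint by a procedure that "provides Newcombe confidence limits with Mantel-Haenszel weights for the common risk difference".

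**The concern.** Φ(min{…}) is the exact joint probability only when Z_TV and Z_MAV have correlation −1. That requires both to be the same estimate, with the same standard error, measured from two known constants. This is true for complications. It is not true for time to resolution, because the TV moves with the estimated placebo median. The SAP recognises this feature for change from baseline, where the TV is 1.2 times the estimated placebo mean, but groups time to resolution with the endpoint whose TV really is fixed.

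If the TV is also treated as fixed in Z_TV, its standard error is too small. The p-value against the TV feeds the Stop and inconclusive probabilities, and Section 5.6 re-sizes Cohort 2 so that the inconclusive probability is at most 20% on all clinical endpoints. An understated inconclusive probability can therefore give too small an extension.

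**Working it through.** **Inputs.** One-sided critical value Φ⁻¹(0.9) = 1.2816. Allocation 1:1:1 and 70 to 80 Cohort 2 subjects at IA#3 (Sections 1.5 and 3), so n₁ = 75, about 25 per arm. Weight w₁ = 75/225 = 1/3 (Section 5.6). Tp = 3 days is the Cohort 1 planning value in Section 1.4. No Cohort 2 median is stated, so 3 to 8 days is an assumed range. For the log-logistic scale, Section 1.4 prints 1/0.65. With variance 3σ²/n per log-median and 48 per arm, σ = 0.65 gives a 96.1–96.5% chance of an effect in the right direction, close to the stated 95%; σ = 1/0.65 gives 77–78%. I use σ = 0.65. Equal arms, no censoring and no covariates are assumed.

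**Error of the test against the TV.** The contrast is μ_H − log Tp − log[(Tp−1)/Tp] = μ_H − log(Tp−1), where μ_H is the log-median for high dose. The derivative of log(Tp−1) with respect to log Tp is Tp/(Tp−1). With variance v per arm, the true variance is v[1 + (Tp/(Tp−1))²]; with a fixed TV it is 2v. The ratio of true to used standard error is k = √{[1 + (Tp/(Tp−1))²]/2}, and the actual error is 1 − Φ(1.2816/k). It does not depend on σ.

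| Tp (days) | (Tp/(Tp−1))² | k | actual error |
|---|---|---|---|
| 3 | 2.250 | 1.275 | 15.7% |
| 5 | 1.563 | 1.132 | 12.9% |
| 7 | 1.361 | 1.087 | 11.9% |
| 8 | 1.306 | 1.074 | 11.6% |

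Simulated AFT fits (4,000 per setting) at Tp = 3 give 18.7% with 25 per arm and 17.6% with 50. With the delta-method standard error, the simulated error is 9.7–10.7% over Tp 3 to 7 days and 25 to 100 per arm.

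**Conditional probabilities, Tp = 3, no observed effect.** TV = log(2/3) = −0.405. The contrast standard error is √(2·3·0.65²/25) = 0.318. So z_TV = 0.405/0.318 = 1.273 with a fixed TV, or 1.273/1.275 = 0.999 corrected; z_MAV = 0.

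- CRV_TV = (1.2816 − √(1/3)·z_TV)/√(2/3) = 0.669 (fixed) or 0.863 (corrected).
- Stop at N = 150 (n₂ = 75, so μ_TV = z_TV): Φ(1.273 − 0.669) = 0.727, or Φ(0.999 − 0.863) = 0.554.
- Go: the MAV term is the smaller, 0 − 1.2816/√(2/3) = −1.570, and Φ(−1.570) = 0.058. With the bivariate formula it is also 0.058.
- Inconclusive: 1 − 0.727 − 0.058 = 0.215, or 1 − 0.554 − 0.058 = 0.388.

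On the SAP's grid of sizes, μ_TV = √((N−75)/75)·z_TV. At N = 180 the fixed-TV version gives Stop Φ(1.507 − 0.669) = 0.799 and inconclusive 0.143, which meets the 20% limit. Corrected, N = 180 gives 0.317, N = 210 gives 0.258 and N = 240 gives 0.210; N = 270 gives Stop Φ(1.611 − 0.863) = 0.773 and inconclusive 0.169. For this endpoint alone, 180 would be chosen where 270 is needed. At Tp = 8 the change at N = 150 is small (0.745 to 0.758).

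**Correlation.** With r = Tp/(Tp−1) = 1.5, ρ = −(1 + r)/(√2·√(1 + r²)) = −2.5/2.550 = −0.98. For change from baseline the SAP's own formula gives −2.2/(√2.44·√2) = −0.996 with equal arms.

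**Complications, 25 per arm, true difference equal to the TV.** Exact binomial error against a nominal 10%:

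| placebo / high dose | plug-in normal | Newcombe (unstratified) |
|---|---|---|
| 10% / 0% | 27% | 7% |
| 12% / 2% | 20% | 10% |
| 15% / 5% | 16% | 10% |
| 20% / 10% | 13% | 10% |

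With 1/25 on placebo and 0/25 on high dose, the plug-in 80% lower limit is −0.090 (excludes the TV) and Newcombe's is −0.125 (does not). With no events in either arm the plug-in standard error is 0 and the statistic is undefined.

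**The case against.** The strongest reply is that Section 5.6 speaks of appropriate contrasts in the same words as for change from baseline, where the placebo error is counted, so Z_TV may already include the error in Tp. The variance is indeed not stated, and the error figures are conditional on its being left out. But if it is included, the correlation is not −1 and Φ(min{…}) does not match the contrast. One of the two needs correcting, although on that reading the numerical effect is small.

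A reader might infer four stronger things that the document does not support.

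- **Stop is always overstated.** It is overstated only when the observed effect is worse than the TV. At the TV both versions give 0.058; beyond it Stop is slightly understated (0.004 against 0.008 at a corrected z_TV of −0.5, Tp = 3, N = 150).
- **Enrichment is distorted.** The enrichment rule uses Go at Interim Analysis 4, with N = 150. There the MAV term governs, and Go is unchanged to three decimals for observed effects of 0, 0.5, 1 and 1.5 times the TV at Tp = 3. The largest change at N = 300 is 0.938 to 0.930.
- **A drug at target would be stopped too often.** The Stop probability is not a stopping rule. Futility at IA#3 uses 80% confidence intervals on at least two clinical endpoints together with viral-load conditional power and the MAV condition, needs both populations, and only guides the monitoring committee.
- **Other endpoints share the defect.** The complications TV is fixed, so Φ(min{…}) is right there, and change from baseline already carries the placebo error.

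For complications, it is fair to say that the planned 80% interval is already Newcombe. The plug-in excess largely fades at the projected sizes: for the four rate pairs tabulated, the exact error is 10.4–11.8% at 50 per arm and 10.4–12.7% at 100. No complication rate is stated that would make the sparse cases likely.

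**Conclusion.** The point holds for one endpoint, time to resolution. The Go formula assumes a known TV, while the TV is estimated from the same data. If Z_TV makes the same assumption, the nominal 10% error becomes about 12% to 16% for placebo medians of 8 down to 3 days, and about 19% in simulation at 3 days with 25 per arm. The practical consequence is an understated inconclusive probability when the observed effect is worse than the TV, and so possibly too small a re-estimated Cohort 2. This is material at Tp = 3 and minor at Tp = 8.

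The error inflation rests on equal arms and on a Cohort 2 median that the SAP does not give. The conditional probabilities also depend on σ = 0.65 and n₁ = 75. The 20% limit applies to all clinical endpoints, so another endpoint could still force a larger size. The complications p-value is a secondary small-sample point, confined to about 25 per arm with few events.

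**What to change.** For time to resolution, state in Section 5.6 that Z_TV tests μ_H − log(Tp−1) with its delta-method variance: the placebo term multiplied by (Tp/(Tp−1))², plus the covariance term from the fitted AFT model where covariates make the two estimates correlated. Compute Go with the bivariate-normal formula already written for change from baseline, using the matching correlation (about −0.98 at Tp = 3 with equal arms).

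For complications, derive the p-values against the TV and MAV from the Newcombe or score method, so that they agree with the 80% interval planned in Section 5.4.2 and are defined when no events occur.

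The cost is a few sentences in the SAP and a few lines of code. No data collection or design feature changes.

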2.1. Visit Windows and Phase Definitions

2.1.1. Analysis Phase Definitions

Analysis phases will be constructed as defined in [Table 2](#).

Table 2: Analysis Phases

Analysis Phase [number]	Start Date/Time	End Date/Time
Screening [1]	00:00 of the date of signing the informed consent form *	1 minute before the first study drug administration in the trial
Treatment [2]	Date/time of first study drug administration in the trial	23:59 of the last day of treatment + 3 days or 23:59 of the cut-off date for the IA, whichever comes first
Follow-up [3]	1 minute after the End of Treatment Phase	23:59 of the day of trial termination (date of last contact) or 23:59 of the cut-off date for the IA, whichever comes first

* For some sites, diagnostic ICF (Dx ICF) is required if RSV infection testing is not part of SOC or the SOC RSV diagnostic assay is not approved for use in the study. The earliest date between Dx ICF and main ICF will be used as a reference.

Assessments will be assigned to analysis phases based on their date/time, but seconds will be ignored overall. If the day part of the start date of the assessment is present but the time part is missing, the assessment will be treated as if it started at 00:00 on the day of the event (unless for Adverse Events see details in [Section 6.1](#)). If the day part of the end date of the assessment is present but the time part is missing, the assessment will be treated as if it happened at 23:59 on the day of the event. No formal imputation will be done, these rules will only be applied to allocate assessments to analysis phases.

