3. INTERIM ANALYSIS AND DATA MONITORING COMMITTEE REVIEW

[figure not shown]
Up to four IAs are planned for this study ([Figure 2](#)):

- i. The first IA will take place when at least 36 subjects from Cohort 1 have completed Day 14 assessments (or discontinued earlier) to evaluate safety and tolerability, PK, and antiviral effect.
- ii. The second IA will take place preferably at the end of a hemispheric RSV season when approximately 70 to 80 subjects from Cohort 1 (regardless of the number of subjects in the subcohort having reached the target of 6 subjects) have completed Day 14 assessments (or discontinued earlier). Depending on enrollment status of Cohort 2, second IA will not be performed if later or too close to the estimated timing of the planned third IA. A futility and population enrichment analysis will be performed on antiviral activity (data from both cohorts combined), to terminate the study for futility, or to enrich the population and limit further enrollment to patients with ≤ 3 days since symptom onset. In addition, clinical course and safety-related endpoints, will be analyzed.
- iii. The third IA will take place preferably at the end of a hemispheric RSV season, when approximately 70 to 80 subjects from Cohort 2 have completed Day 14 assessments (or discontinued earlier) and will include data from Cohort 1 and Cohort 2. This IA will include a futility and population enrichment analysis on antiviral activity (data from both cohorts combined) and clinical endpoints (data from Cohort 2 only), as well as a sample-size re-estimation for Cohort 2 based on clinical endpoints.
- iv. The fourth IA will only take place if after third IA, decision is to increase number of subjects for Cohort 2. This IA will take place preferably at the end of a hemispheric

RSV season, after approximately 150 subjects in Cohort 2 completed Day 14 of assessments (or discontinued earlier) and will also include Cohort 1 subjects. The primary analysis on antiviral activity will be performed during this fourth IA and effects of JNJ-53718678 on clinical course endpoints, next to endpoints related to safety, PK and PK/PD, will be analyzed to support early Phase 3 plans.

The final analysis is planned when all subjects from Cohort 1 and Cohort 2 have completed the study (or discontinued earlier). If no extension of Cohort 2 is required, the final analysis may coincide with the primary analysis.

Figure 2: Overview of Different Planned Analyses in Study 53718678RSV2002

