RSV-related complications: modified definition	Any subject who experienced at least one emergent adverse event included in the list of complications below will receive code 1, subjects who did not experience any of the specified emergent adverse events will receive code 0.

Measurement	Formula
[study physician-identified complications]	
 Respiratory complications: respiratory failure, respiratory distress, apneic attacks, bronchiolitis, bronchial obstruction, pneumonia, asthmatic crisis. Infectious complications: otitis media, bacterial respiratory tract infections, sepsis; Cardiovascular complications: arrhythmia, cardiogenic shock, hemodynamic instability, congestive cardiac failure; Acid-base or electrolyte complications: metabolic acidosis (serum $\text{HCO}_3^- < 16$), metabolic alkalosis (serum $\text{HCO}_3^- > 30$) 
The final list of emergent adverse events to be considered as per modified definition of RSV-related complications, will be reviewed and documented prior to a database lock.
 
The modified definition for RSV-related complications will primarily be used as follows:
 
 from IA#3 and onwards in any decision rule that requires RSV-related complications data
Need for antibiotics related to complications associated with RSV: Investigator assessment [categorical]	
Need for antibiotics is defined as 'Yes' if the answers to the following 2 questions on the Adverse Events eCRF are answered with 'Yes' (Yes to both questions):
 
 Is this AE a complication related to the current respiratory infection? Concomitant or additional therapy given for this adverse event? 
And if the answer to the following question on the Concomitant Medications eCRF for the related medication is answered with 'Yes'.
 
 Was this medication an Antibiotic?

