- The conditional power at IA#4 is $<50\%$ to demonstrate antiviral activity of JNJ-53718678 compared with placebo based on the MCP-Mod trend test on viral load at 1-sided alpha=2.5% based on combined data from Cohort 1 and Cohort 2.

AND

- 80% 2-sided confidence interval on at least 2 key clinical course endpoints excludes effects as good as the TV based on data from Cohort 2 only

AND

- None of the 80% 2-sided confidence intervals on any key clinical course endpoint excludes effects as bad as the MAV based on data from Cohort 2 only

For viral load, the conditional probability of success at IA#4 using combined data from Cohorts 1 and 2 will be calculated assuming i) no enrichment and ii) enrichment as described below.

In both cases, the conditional probability of success will be set to 1 if the 1-sided p-value for the MCP-Mod trend test is less than 2.5% at IA#3, as success has already been reached. Otherwise, the conditional Type I error will be calculated using the inverse-normal combination approach:

$$\rho = 1 - \Phi \left(\frac{\Phi^{-1}(0.975) - \sqrt{w_1} \Phi^{-1}(1 - p_{Full})}{\sqrt{1 - w_1}} \right)$$

where:

- p_{Full} represents the 1-sided p-value for the MCP-Mod trend test for the full population at IA#3
- $w_1 = n_1 / n$
- n_1 represents the total number of randomized patients in Cohorts 1 and 2 at the time of IA#3
- $n = 294$, the planned total number of randomized patients in Cohorts 1 and 2 at IA#4

Given the conditional Type I error, the critical value for the MCP-Mod test based on new data from IA#4 only will be calculated. The conditional probability of success at IA#4 will be calculated under the observed test statistic at IA#3 (Z_1), adjusted for the sample size of the new data at IA#4 as:

$$CP_x = 1 - P(\bigcap_{i=1}^3 \{Z_{i,2} \in (-\infty, CRV)\})$$

where:

$$Z_2 \sim N \left(\mu_{Z,2} = \sqrt{\frac{n_2}{n_{1,x}}} Z_{1,x}, corr = corr_{MCPx} \right)$$

and:

- x corresponds to the decision not to enrich / to enrich at IA#3
- $Z_{1,x}$ represents the vector of observed MCP-Mod test statistics at IA#3 (Linear, Emax and Exponential models) based on the population of interest (full population for no enrichment and the sub-population with symptom onset ≤ 3 days for enrichment).
- Z_2 represents the vector of observed MCP-Mod test statistics for the second stage.
- $Z_{i,2}$ represents the observed MCP-Mod test statistic for the second stage (based on the new data at IA#4) for model i.

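### At IA#3, children who have not reached the endpoint day are counted as stage-1 information, and complications are coded 0 without any minimum follow-up, so conditional power is distorted if enrolment is still open

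*SAP*

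**What the plan says.** SAP Section 3 times the third interim for "when approximately 70 to 80 subjects from Cohort 2 have completed Day 14 assessments (or discontinued earlier"). Section 1.4 does not restrict the data to those children. The endpoint selection there is "Based on all clinical course data from Cohort 2 available at the time of the cut-off for the third IA".

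In Section 5.6, n1,x for the clinical endpoints "represents the number of randomized patients in Cohort 2 at the time of IA#3 for the population of interest". For viral load, n1 "represents the total number of randomized patients in Cohorts 1 and 2 at the time of IA#3". These counts set the weight w1 (n1/225 for clinical endpoints, n1/294 for viral load), the stage-2 size n2 (N minus the full-population n1) and the drift √(n2/n1,x). For the Day 8 score only, the correlation formula uses a different basis: its high-dose count "represents the number of Cohort 2 subjects in the high dose group that were included in the analysis at IA#3".

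For complications (modified definition, Section 5.4.1, Table 22), "subjects who did not experience any of the specified emergent adverse events will receive code 0". Section 5.4.2 counts events over treatment and follow-up, and Section 1.2 runs follow-up to about Day 28. Section 2.1.1, Table 2, ends the treatment and follow-up phases no later than the cut-off: "23:59 of the cut-off date for the IA, whichever comes first". No minimum follow-up is stated.

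**The concern.** A child randomized just before the cut-off contributes little or nothing to the IA#3 p-value of an endpoint that has not yet been observed. The formulas still place that child in stage 1 and deduct the child from stage 2, so the child's information is credited to neither stage. By IA#4 the child will have data, and those data belong to stage 2.

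The results feed stated rules. Enrichment is considered if at least two of four endpoints have conditional power below 50%. Viral-load conditional power below 50% is one of three conditions for futility. The probability of an inconclusive result, which is to be held to 20%, determines the Cohort 2 sample size.

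Complications have a second problem. A child just past Day 14 with no event is coded like one followed to Day 28, so the observed difference between arms shrinks towards zero, that is, towards excluding the -0.1 target.

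**Working it through.** **Inputs from the SAP.** Go/Stop confidence is 80% two-sided, so z = 1.2816. N is 150 for Cohort 2 at IA#4. The w1 denominator is (150+300)/2 = 225, which reproduces the stated figure. Viral load uses 144+150 = 294, also as stated. The planning table in Section 5.2.3.2 has about 75 in Cohort 2 and 144 in Cohort 1 at IA#3, total 219. The SAP states no conditional power value, so there is none to reproduce.

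**Assumed.** All Z values, complication rates and numbers of children short of the endpoint. For scale, accrual of 75 children evenly over 90 to 150 days leaves 75×14/150 = 7 to 75×14/90 ≈ 12 short of Day 14. The 7 days before Day 8 give about 4 to 6, and the 4 days before Day 5 about 2 to 3.

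**Formulas (no enrichment).**
- MAV limb: Φ(√(n2/n1)·Z_MAV − [1.2816 − √w1·Z_MAV]/√(1−w1))
- TV limb: Φ([1.2816 − √w1·Z_TV]/√(1−w1) − √(n2/n1)·Z_TV)
- Go is the smaller limb; Stop is 1 minus the TV limb. The Day 8 score uses a bivariate normal version.

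**1. MAV limb binds** (Z_MAV = 1, Z_TV = 0; the Z values come from 75 children with data).
- n1 = 75: w1 = 0.3333, n2 = 75, drift 1.000, critical value (1.2816−0.5774)/0.8165 = 0.8625, so Go = Φ(0.1375) = 0.555.
- n1 = 95: w1 = 0.4222, n2 = 55, drift 0.7609, critical value 0.8311, so Go = Φ(−0.0702) = 0.472.

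| Children without endpoint data | n1 used | Go |
|---|---|---|
| 0 | 75 | 0.555 |
| 4 | 79 | 0.537 |
| 10 | 85 | 0.512 |
| 12 | 87 | 0.503 |
| 20 | 95 | 0.472 |

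**2. TV limb binds** (Z_MAV = 1.2, Z_TV = 1.0). Go rises from 0.445 at n1 = 75 to 0.488 at 85 and 0.528 at 95. With N = 300 and Z values of 1.0 and 0.5, it rises from 0.637 to 0.700 at n1 = 95. With Z_TV = 1 and N = 150, Stop falls from 0.555 to 0.472.

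**3. Viral load** (reduced to a single contrast, z = 1.96, Z = 1.6). n1 = 219 gives 0.417. Ten further children all lacking data (n1 = 229) give 0.377. If only three of the ten are short of Day 5 (n1 = 222), the result is 0.405.

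**4. Complications** (true rates 20% on placebo and 10% on high dose; 25 children per arm complete and 7 per arm recent, so n1 = 96).
- If none of the recent children's risk has been seen, the observed rates are 25×0.20/32 = 0.156 and 25×0.10/32 = 0.078. The difference is −0.078 instead of −0.10.
- SAP rule: Go 0.455, Stop 0.106. If half their risk has been seen: Go 0.504, Stop 0.069.
- The same 96 children fully followed: Go 0.553, Stop 0.045.
- Only the 75 complete children, n1 = 75: Go 0.555, Stop 0.058.
- Coding as 0 but keeping n1 = 75: Go 0.540 (none seen) or 0.592 (half seen).

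**5. Basis of n1.** Suppose 75 are randomized, all have reached the endpoint day, and 68 are in the ITT-i set. With Z = 1, n1 = 75 and n2 = 75 give 0.555. Using 68 and 150−68 = 82 gives 0.588, because children permanently excluded are counted as future patients. For viral load with 219 randomized and 197 analysed, the same substitution moves 0.417 to 0.496.

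**The case against.** Several counter-arguments stand.

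- **Direction.** A reader might infer that conditional power is always understated. Step 2 shows that Go is overstated when the TV limb binds, and step 4 shows that coding as 0 can, on its own, raise Go slightly.
- **Endpoints.** A reader might also infer that all four endpoints treat recent children as complete. Only complications do. Unresolved symptoms are censored, and the Day 8 score and viral load use repeated-measures models; there only n1 is affected.
- **Information already in hand.** Most children short of Day 14 already have Day 5 or Day 8 data. In step 3 that cuts the viral-load effect from 4 points to about 1.
- **Number of recent children.** The SAP prefers IA#3 at the end of an RSV season, states that Cohort 1 enrolment is complete, and plans about 75 in Cohort 2, the same as the completer target. Recruitment may therefore be low at the cut-off, although end of season is only a preference.
- **Internal mismatch.** The count "in the high dose group that were included in the analysis at IA#3" differs in basis from n1,x, but enters only a correlation that depends on the ratio of the arms: −0.9959 for 25/25, 29/29 and 24/27. The inconsistency has almost no numerical effect.
- **Decisions.** The other two futility conditions are confidence intervals that do not use n1, futility must be met in both populations, and the committee's rules are for consideration. Truncation is equal across arms, so a null comparison of complications is not biased.

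None of this supplies a rule for children who have not reached the endpoint day.

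**Conclusion.** The concern holds in a limited form and should be corrected. The n1 definition and the missing follow-up rule are plain in the text.

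If enrolment is open at the cut-off, conditional power is understated for viral load with a positive trend and for Go when the MAV limb binds: by about 2 to 8 points for 4 to 20 Cohort 2 children without endpoint data, at Z = 1 and N = 150. Go is overstated when the TV limb binds. The size rests on assumed Z values and on a count the SAP does not give; the n1 effect is zero if no such children exist.

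The follow-up problem for complications does not need open enrolment, since a child at Day 14 has not finished a window that runs to about Day 28. It pulls the observed difference towards zero. The documents do not support a claim that the interim would probably reach a wrong futility or enrichment decision, only that an endpoint near 50% can be placed on the wrong side.

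**What to change.** In Section 5.6, define n1,x (and n1 in w1) for each endpoint as the number of randomized subjects in the population of interest who, by the IA#3 cut-off, have reached that endpoint's assessment day or discontinued earlier: Day 5 for viral load, Day 8 for the symptom score, Day 14 for time to resolution and complications. Base the IA#3 p-value on those subjects. Set n2 to N minus that number for the full population, so that n1, n2 and N all stay on the randomized basis. Do not use N minus the ITT-i analysed count, for the reason in step 5.

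For complications at IA#3 and IA#4, include only children who completed Day 14 or discontinued, and count events through Day 14. Keep the full follow-up window for the final analysis.

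The cost is SAP wording and a small programming change. Complications after Day 14 would not be counted at the interims, and partial data from the most recent children would not enter the IA#3 p-values.
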